## Objective

Our objective is to assess the effectiveness of blogshots to increase parent awareness, knowledge and expectations with respect to CWC recommendations that align with common childhood conditions.

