## Research Methods/Procedures

This is a multi-method study including a randomized control trial (RCT) and qualitative interviews. While the RCT will provide quantitative estimates of effectiveness, the qualitative component will help us understand how the intervention works. Ethics approval will be sought through the University of Alberta Human Research Ethics Board (HREB). The trial will be registered on the ClinicalTrials.gov database after ethics approval.

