**Figure 1: Study Design**

**Blogshot Development:** Six blogshots were developed with the assistance of a graphic designer. Members of the P-PAG provided feedback on the language, design and content of the blogshots.

**Online Questionnaire Development:** The research team developed four questionnaires (baseline and 3 follow-up questionnaires). The questionnaires consist of multiple choice knowledge questions based on the information presented in the blogshots, questions about participant’s intentions for managing common acute childhood conditions and actions participants took if their child developed symptoms of one of the conditions from the blogshot during the duration of the study. A series of 7 questions about the usability of the blogshots will be included in the questionnaire as well.

The questionnaire is designed and housed in the Nooro platform (<https://nooro.com>). An overview of each question category is listed below:

**Baseline Questions:** Four baseline questions will be included about parent’s experience with the common acute childhood conditions included in the blogshots as well as number of times they went to the emergency department or received a prescription for antibiotics for their child. A question about information seeking is also included. **These questions are asked at baseline.**

**Knowledge Questions:** Each topic will have three “core” knowledge questions that will be included at baseline and all three follow-up questionnaires. An additional knowledge question will be included for each topic in which a participant received a blogshot. For example, group A will

receive one extra question for the sore throat swab, cough and cold medication and bronchiolitis topic and group B will receive an extra question on acute otitis media, asthma exacerbations and sore throat. **These questions are asked at baseline, follow-up 1, follow-up 2 and follow-up 3.**

**Expectation Questions:** Each blogshot topic will have 1 expectation question that asks parents about their expectations from a healthcare provider on the management and treatment of each condition. **These questions are asked at baseline and follow-up 1.**

**Intention Questions:** Each blogshot topic will have one intention question that asks parents about their intentions on the management and treatment of each condition. **These questions are asked at baseline and follow-up 1.**

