## Outcomes

The will be knowledge immediately after the campaign; we will compare change from baseline between groups (i.e. average change in knowledge scores specific to CWC recommendations, expecting that knowledge will improve with respect to the content received). Secondary outcomes will be intentions, expectations of care and usability of the blogshots. We will explore if outcomes were influenced by whether a child had one of the conditions (and identify actual behaviour). All outcomes will be assessed both quantitatively through questionnaire responses and qualitatively through the semi-structured interviews.

The outcomes will focus on the following 5 domains:

**Knowledge:** Knowledge will be assessed by comparing participant's scores on baseline questionnaire to follow-up questionnaire 1 (knowledge change) and comparing scores to follow-up questionnaires 2 and 3 (knowledge retention).

**Expectations:** Participants will be asked questions about their expectations of healthcare professionals at baseline and follow-up 1 questionnaires. We will compare at baseline and follow up to assess if the blogshots led to a change in expectations of healthcare professionals.

**Intentions:** Participants will be asked questions about their intentions at baseline and follow-up 1 when they seek healthcare i.e. are they seeking antibiotics from a healthcare professional.

**Actions:** Participants will be asked about actions they took during the course of the study in follow-up questionnaires 2 and 3. For example if their child had symptoms related to information in the blogshot and the actions they took i.e. went to a physician, filled a prescription for antibiotics, etc.

**Usability of the blogshots:** Participants will complete usability questions about the blogshots focusing on topics such as if the blogshots increase knowledge, aid in decision-making and are relevant to parents. This will be completed at follow-up 1.

The semi-structured interviews will include questions on all 5 of these domains to clarify, expand on and provide to context to the questionnaire responses.

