## Plan for Data Analysis

**Questionnaire Data:** Demographic data will be collected to evaluate how representative our sample is to the Canadian population. We will use descriptive statistics, including numbers, frequencies, and means, to present demographic data. Group differences will be evaluated using independent t-test or chi squared and baseline and follow-up will be evaluated using paired t-tests or Wilcoxon signed rank test, dependent on distribution of data. In all analyses, statistical uncertainties will be expressed in 95% two-sided confidence intervals. A p value of <0.05 will indicate statistical significance. Analyses will be conducted based on intention-to-treat[20].

**Interview Data:** The project coordinator will perform an inductive thematic analysis of the interview data[21]. Interview coding and analysis will occur concurrently with data collection using an iterative approach. In this approach, data will be categorized into codes, forming categories that are then combined into themes that can be thoroughly described in the results. Lincoln and Guba's criteria will be used to establish trustworthiness of the analytic process[22]. Qualitative data analysis software NVIVO will be used to organize and code the data[23].

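### The expectations outcome, as most naturally read, draws a causal conclusion from a before-after comparison; the plan should name the between-arm contrast as its basis (minor)

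*Combined protocol and SAP*

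**What the plan says.** The objective is to "assess the effectiveness of blogshots to increase parent awareness, knowledge and expectations", so expectations are part of the main question even though the Outcomes section ranks them as secondary. Research Methods/Procedures states that "the RCT will provide quantitative estimates of effectiveness".

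For the primary outcome, knowledge right after the campaign, the Outcomes section is explicit: "we will compare change from baseline between groups". The other outcomes are described differently:

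- **Expectations:** "We will compare at baseline and follow up to assess if the blogshots led to a change in expectations of healthcare professionals". The verb is causal and no arm is named. The questionnaire description adds: "Each blogshot topic will have 1 expectation question that asks parents about their expectations from a healthcare provider". It gives no answer scale.
- **Intentions:** "Participants will be asked questions about their intentions at baseline and follow-up 1 when they seek healthcare". This gives timing only.
- **Knowledge:** "scores on baseline questionnaire to follow-up questionnaire 1 (knowledge change) and comparing scores to follow-up questionnaires 2 and 3 (knowledge retention". No arm is named in this paragraph, although its follow-up 1 part is the outcome compared between groups in the section's opening.

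The Plan for Data Analysis puts both kinds of test in one sentence: "Group differences will be evaluated using independent t-test or chi squared and baseline and follow-up will be evaluated using paired t-tests", with the Wilcoxon signed-rank test as the alternative to the paired t-test. It ties neither kind to a named outcome and does not say which supports a conclusion about effect.

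**The concern.** Set the expectations sentence beside the analysis sentence. The first compares baseline and follow-up; the second evaluates baseline and follow-up with paired tests. Followed literally, a significant paired result would be taken as showing that the blogshots changed expectations.

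A paired test within an arm asks whether answers moved, not why. Participants answer the same expectation items twice, five weeks apart. Repetition, the passage of time or season could move answers in both arms. Randomization removes such shared change from a between-arm contrast but not from a paired one. At stake is whether a conclusion on a construct in the objective uses the randomization at all.

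**Working it through.** **1. The plan's own calculation.** Inputs from the Sample Size paragraph: SD 2.0, 80% power, 64 per group; two-sided 5% from the Plan for Data Analysis. The score range is not given, so I take the 10% difference as 1.0 point (a 10-point scale). Then n = 2 × (1.960 + 0.842)² × 2.0² / 1.0² = 62.8, or 63 per group; the t-test version gives 63.8, or 64. The stated 64 reproduces as a two-sided between-group comparison of knowledge scores. No calculation is given for expectations.

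**2. Illustration for one expectation item.** Assumptions, none from the documents: yes/no answer; 50% yes at baseline and 40% at follow-up in both arms, so no blogshot effect; correlation φ of 0.3, 0.5 or 0.7 between the two answers. I use 64 completers in an arm.

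- Probability of yes at both times = 0.5 × 0.4 + φ × √(0.5 × 0.5 × 0.4 × 0.6).
- At φ = 0.5 this is 0.200 + 0.5 × 0.245 = 0.3225. Yes-to-no is 0.5 − 0.3225 = 0.1775 and no-to-yes is 0.4 − 0.3225 = 0.0775.
- On 0/1 differences the signed-rank test equals McNemar without continuity correction. Its expected z is 64 × (0.1775 − 0.0775) / √(64 × 0.255) = 6.4 / 4.04 = 1.58. The chance of exceeding 1.96 is about Φ(1.58 − 1.96) = Φ(−0.38) = 0.35.

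Simulated values for a 10-point shared fall, confirmed by exact enumeration to within 0.002:

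| Test | φ = 0.3 | φ = 0.5 | φ = 0.7 |
|---|---|---|---|
| Signed-rank, one arm | 28% | 35% | 53% |
| Exact McNemar, one arm | 20% | 27% | 42% |
| Between-arm chi-squared at follow-up | about 5% | about 5% | about 5% |

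The result depends on the assumed fall. For the signed-rank test, a 5-point fall gives 11% to 16% and a 15-point fall 55% to 93%. With 30% yes at baseline, a 10-point fall gives 34% to 68%. The between-arm test stays near 5% because the true difference between arms is zero.

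**3. Price in precision.** For a score with SD 2.0 and 64 per arm, at correlation r, the SD of change is 2.0 × √(2(1 − r)), which is 2.37, 2.00 or 1.55 for r = 0.3, 0.5 or 0.7. The 95% half-widths are:

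- Paired, t × SD of change / √64: 0.59, 0.50, 0.39.
- Between-arm change, t × SD of change × √(2/64): 0.83, 0.70, 0.54. This is about √2 times the paired width, or 40% wider.
- Between-arm with baseline adjustment, t × 2.0 × √(1 − r²) × √(2/64): 0.67, 0.61, 0.50. This is 13% to 29% wider than paired.

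For the yes/no illustration, the half-width is 14, 12 or 9 percentage points paired, against 17 for the between-arm difference at follow-up.

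**The case against.** The strongest reply is that a between-arm analysis is what the authors mean. The expectations sentence gives its verb no object, and comparing at two time points can mean comparing the groups at each. The Knowledge paragraph uses similar before-after language for an outcome that the same section compares between groups, so these paragraphs may only describe timing. The plan names group-difference tests, calls for intention-to-treat analysis and makes the randomized trial the source of effectiveness estimates. This stands as a reason for caution about intent. It does not supply the missing statement, and the only tests the plan attaches to baseline and follow-up are paired.

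A second reply is that both arms receive related content. Sore throat and asthma appear in both topic lists, and antibiotic messages make up one Group A topic and all three Group B topics. Shared change could therefore be partly a real blogshot effect, and the between-arm contrast could understate it. This also stands, as a caveat on the fix. It does not rescue the paired test, which cannot separate such spillover from the effect of repeating the items.

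A third reply is that the percentages follow from the chosen drift. That is correct: they show how a paired test behaves, not a risk measured from this plan.

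A reader might also infer that the plan commits to uncontrolled effect claims for intentions and knowledge retention. The documents do not support that: neither carries causal wording, and retention may be a descriptive question about how much knowledge is kept. Their contrast is simply unassigned.

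**Conclusion.** The point holds for expectations, as a minor one. On the most natural reading, a causal conclusion rests on a before-after comparison in a trial that has a randomized comparator available. If the paired test is used that way, shared change would be credited to the blogshots. The illustrated rate of 28% to 53% (20% to 42% with the exact test), against about 5% between arms, rests on an assumed answer scale, a 10-point shared fall from 50%, and assumed correlations. The size moves with those choices; the direction does not, provided there is some shared change.

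The plan should not be described as definitely intending an uncontrolled analysis. For intentions and later knowledge the finding is missing detail only. The primary outcome has its own stated between-group contrast and is unaffected.

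**What to change.** In Outcomes and in the Plan for Data Analysis, state that the effect conclusion for expectations at follow-up 1 is the between-arm comparison: the arm sent a topic versus the arm not sent it.

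- For scores, use the between-arm difference in change from baseline, or the difference adjusted for baseline. For categorical answers, use the chi-squared comparison of arms at follow-up, which the plan already names.
- Label paired within-arm tests descriptive.
- Apply the same rule to any effect claim on intentions or on knowledge at follow-ups 2 and 3. For knowledge, use only the core items, since the extra items go only to the arm that received the topic.
- Confirm that both arms answer all expectation and intention items.
- State that sore throat, asthma and antibiotic messages overlap between arms, so the contrast may understate an effect.
- Reconcile the topic lists. Study Design: RCT places acute asthma exacerbations in Group A and bronchiolitis in Group B; the Knowledge Questions text gives Group A the extra bronchiolitis question and Group B the asthma one. Until this is settled, the comparison arm for those topics is undefined.

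The cost is wording plus wider intervals than paired ones: about 40% wider for change scores, less with baseline adjustment. Adjusting a categorical answer for baseline would need a model the plan does not name, so it is optional.

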## Plan for Data Analysis

**Questionnaire Data:** Demographic data will be collected to evaluate how representative our sample is to the Canadian population. We will use descriptive statistics, including numbers, frequencies, and means, to present demographic data. Group differences will be evaluated using independent t-test or chi squared and baseline and follow-up will be evaluated using paired t-tests or Wilcoxon signed rank test, dependent on distribution of data. In all analyses, statistical uncertainties will be expressed in 95% two-sided confidence intervals. A p value of <0.05 will indicate statistical significance. Analyses will be conducted based on intention-to-treat[20].

**Interview Data:** The project coordinator will perform an inductive thematic analysis of the interview data[21]. Interview coding and analysis will occur concurrently with data collection using an iterative approach. In this approach, data will be categorized into codes, forming categories that are then combined into themes that can be thoroughly described in the results. Lincoln and Guba's criteria will be used to establish trustworthiness of the analytic process[22]. Qualitative data analysis software NVIVO will be used to organize and code the data[23].

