### Study Design: RCT

Participants will be randomized to two groups: Group A or Group B; each will receive messages over 4 weeks that will consist of blogshots for different CWC recommendations [18]. Participants who complete the baseline questionnaire will receive one blogshot via email every week for three weeks and the fourth week will include a summary of all three blogshots. This will be automated through the Nooro platform. Through the Nooro platform we will monitor if participants have opened the email and viewed the blogshot. If an email has not been opened for 3 days, a reminder email will be sent. At the end of the four-week campaign, participants will be asked to complete a follow-up questionnaire after the intervention at week 5 and then at three and six months post-intervention. The group topics will be:

Group A;

- *Don't routinely do a throat swab when children present with a sore throat if they have a cough, rhinitis, or hoarseness;*
- *Don't recommend the use of cough and cold remedies in children under six years of age;*
- *Don't use antibiotics for acute asthma exacerbations without clear signs of bacterial infection.*

[figure not shown]
Group B;

- *Don't routinely use antibiotics in children with uncomplicated sore throats;*
- *Don't prescribe antibiotics in adults with bronchitis/asthma and children with bronchiolitis;*
- *Don't use antibiotics in adults and children with uncomplicated acute otitis media.*

**Randomization:** Blocked randomization with randomly chosen block sizes will be used to ensure equal distribution of participants to each study arm. The blocked randomization sequence will be computer generated. Parents will be randomized to either group A or group B when completing the demographic and baseline questionnaire on the electronic platform.

**Sample Size:** We will aim to recruit 180 parents (90 participants per group). This is based on assuming a 10% difference between groups in knowledge scores and a standard deviation of 2.0

with 80% power. This would require 64 participants per group and we have increased this number by 25% to allow for dropouts.

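### On a knowledge score built from the core items common to both arms, ANCOVA would be at least as precise as the planned t-test on change, at no cost in data; the plan must first define that score

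*Combined protocol and SAP*

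**What the plan says.** Under Outcomes, the leading outcome is knowledge immediately after the campaign: "we will compare change from baseline between groups". The same sentence adds "expecting that knowledge will improve with respect to the content received". The Plan for Data Analysis then states: "Group differences will be evaluated using independent t-test or chi squared". No baseline-adjusted model appears anywhere in the document.

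The Knowledge Questions paragraph (under Online Questionnaire Development) gives each topic three core "knowledge questions that will be included at baseline and all three follow-up questionnaires". It continues: "An additional knowledge question will be included for each topic in which a participant received a blogshot". So there are core items tied to topics, and further items tied to what a participant was sent. Neither this paragraph, Outcomes nor the Plan for Data Analysis says which items make up the primary score.

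The topic lists also disagree. Study Design: RCT puts the asthma recommendation in group A's list ("use antibiotics for acute asthma exacerbations without clear signs of bacterial infection") and bronchiolitis in group B's. The Knowledge Questions paragraph says group A will "receive one extra question for the sore throat swab, cough and cold medication and bronchiolitis topic" and gives the asthma extra to group B.

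**The concern.** A t-test on change subtracts the whole baseline score, which fixes the slope of follow-up on baseline at 1. If the true slope is lower, as is usual for a short test taken twice, this over-corrects and adds noise. ANCOVA estimates the slope from the data. The baseline score is already collected, so the lost precision is avoidable.

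The advantage depends on baseline being the same test in both arms. The phrase about content received, and the arm-specific extra questions, leave open a score on which each arm is tested on different material. The choice of method therefore cannot be separated from the definition of the score.

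**Working it through.** **Inputs from the document.** SD 2.0, 80% power, 64 per group and a 10% difference (Sample Size); two-sided 95% intervals and p < 0.05 (Plan for Data Analysis); three core items per topic and three topics per arm, hence 9 core items per topic set and 18 in all.

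**Assumed, because the document does not give them.** The baseline-to-follow-up correlation ρ (0.3, 0.5, 0.7); the ratio k of follow-up SD to baseline SD; and whether SD 2.0 describes one score or the change.

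**1. The plan's own figure.** n per arm = 2(1.960 + 0.842)² × 2.0² / δ². With δ = 1.0 this is 62.8, so 63; the exact t-test gives 63.77, so 64. The stated 64 therefore reproduces if the difference is 1.0 point.

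**2. Is baseline usable as a covariate?** "Parents will be randomized to either group A or group B when completing the demographic and baseline questionnaire". Blogshots go only to those who complete that questionnaire, so the baseline score precedes exposure. On shared items its expected value is the same in both arms.

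**3. Variance.** With baseline SD σ₀ and follow-up SD σ₁:
- change score: σ₀² + σ₁² − 2ρσ₀σ₁
- ANCOVA: σ₁²(1 − ρ²)
- difference: (σ₀ − ρσ₁)², which is never negative and is zero only when the slope ρσ₁/σ₀ equals 1.

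Ratio of ANCOVA to change = k²(1 − ρ²) / (1 + k² − 2kρ):

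| k | ρ = 0.3 | ρ = 0.5 | ρ = 0.7 |
|---|---|---|---|
| 0.8 | 0.502 | 0.571 | 0.628 |
| 1 | 0.65 | 0.75 | 0.85 |
| 1.25 | 0.784 | 0.893 | 0.981 |

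At k = 1.25 and ρ = 0.8 the slope is 1.25 × 0.8 = 1 and the ratio is 1.000: no gain.

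**4. Power at 64 per arm, difference 1.0, k = 1** (noncentral t; df 126 for the t-test, 125 for ANCOVA).
- SD of change 2.0: the ANCOVA residual SD is 2.0 × √((1 + ρ)/2) = 1.612/1.732/1.844. Power is 80% for the t-test and 94/90/86% for ANCOVA.
- SD 2.0 of a single score: t-test 66/80/95%, ANCOVA 84/90/98%.

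**5. Which common score?** Suppose each arm gains g on its own topics and nothing on the other arm's. On group A's nine items the between-arm difference is g. On the 18-item sum it is g − g = 0. The two topic sets must be scored separately.

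**6. What if each arm is scored on its own content?**
- *ANCOVA.* If the two tests differ by 1.0 point at baseline (assumed), with equal SDs and no learning, it reports a false difference of (1 − ρ) × 1.0 = 0.70/0.50/0.30. Simulated at 64 per arm with a single-score SD of 2.0, it rejects 51/34/21% of the time.
- *Change score.* It holds 5% in that no-learning case. It does not hold it when bounded tests of different difficulty both improve. With nine items, baseline means of 5.4 and 6.6, and the same logit gain of 0.5/1.0/1.5 in both arms (all assumed), simulation gives false differences of about 0.18/0.39/0.59 point and rejection of 9/22/46%.
- *Either method.* If both arms learn equally, the contrast is g − g = 0 however well the blogshots work.

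**7. Sharing alpha.** If both topic sets are primary at 0.025 each (difference 1.0, SD of change 2.0, 64 per arm), power is 71% for the t-test and 89/84/79% for ANCOVA.

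**The case against.** The best defence is that the planned test is a legitimate one: randomisation makes it unbiased on a common score, and the sample size reproduces for it. That stands. A reader might infer that the primary analysis is invalid; nothing in the document supports this. The size of the gain rests on quantities the document omits, and over the values tabulated it runs from about half the variance down to almost nothing. That stands too, and it is why this is an improvement rather than an error.

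A reader might also infer that the trial is underpowered. If 10% means 10% of nine items, the difference is 0.9 point, and the t-test at 64 per arm has 71% power (ANCOVA 88/83/78%). But that is one reading of the percentage, at exactly 64 completers. With 80 completers per arm, from the 90 to be recruited, it is 81%. If 10% means 1.2 points (nine core items plus three extras), it is 92% at 64. The document does not settle which is meant.

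A third tempting inference is that the change score is a safe fallback if own-content scoring is kept. Step 6 shows that it is not.

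Finally, the document gives no detail on missing follow-up 1 scores or on randomised parents without a baseline score. That is missing detail; it shows no bias and is not part of this point.

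**Conclusion.** The point holds as a free improvement in efficiency. On a core-item score shared by both arms, ANCOVA is in large samples with equal arms never less precise than the planned test. With equal SDs its variance is 35/25/15% lower at ρ = 0.3/0.5/0.7. With SD of change 2.0 and a 1.0-point difference, power at 64 per arm rises from 80% to 94/90/86%. The correlation, the SD ratio and the meaning of SD 2.0 are assumptions, and the gain vanishes when the slope on baseline is 1.

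The recommendation is conditional on the score. The wording about content received leans towards own-content scoring but does not define it, and such a score does not support a between-arm comparison under either method.

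**What to change.** First reconcile the topic lists in Study Design: RCT with the Knowledge Questions paragraph on which arm has asthma and which has bronchiolitis. The topic sets cannot be scored until that is settled.

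Then, in Outcomes and the Plan for Data Analysis:
- Define the primary score from core items asked identically in both arms at baseline and follow-up 1. Exclude the arm-specific extra questions.
- Score group A's topics and group B's topics separately, nine core items each.
- Name one topic set as primary, or state how alpha is shared between the two.
- Analyse the follow-up 1 score by ANCOVA on arm and baseline score, by assigned group, reporting the adjusted mean difference with its 95% confidence interval.
- Do not use an own-content score that differs by arm for the between-arm comparison.

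The cost is wording in two sections and one degree of freedom. No new data or visits are needed. Sharing alpha, if chosen, lowers power under either method, so naming a single primary topic set is the cheaper choice.

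### Expectations and intentions have no defined score, so the plan leaves room for up to 12 single-question tests at an unadjusted 0.05, each with little power

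*Combined protocol and SAP*

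**What the plan says.** The Outcomes section of the combined protocol and SAP states: "Secondary outcomes will be intentions, expectations of care and usability of the blogshots". Under Study Design: RCT, the questionnaire description gives the content of the first two: "Each blogshot topic will have 1 expectation question that asks parents about their expectations from a healthcare provider" and "Each blogshot topic will have one intention question that asks parents about their intentions". Six blogshots were made, three per group, so there are six expectation and six intention questions. Both sets are asked at baseline and follow-up 1 only.

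The Plan for Data Analysis names an independent t-test or chi-squared test for group differences, and a paired t-test or Wilcoxon signed rank test for baseline against follow-up. It does not tie any test to any outcome. It adds that "statistical uncertainties will be expressed in 95% two-sided confidence intervals" and that "A p value of <0.05 will indicate statistical significance".

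The plan speaks of scores for knowledge only. For expectations and intentions it gives no answer format, no scoring, no unit of analysis and no rule for several tests. The sample size also rests on knowledge alone: "This is based on assuming a 10% difference between groups in knowledge scores and a standard deviation of 2.0". The result is 64 per arm for 80% power, before an allowance for dropouts.

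**The concern.** With no score defined and one threshold for all analyses, the analyst may test each of the 12 questions between arms, or choose the unit of analysis after seeing the answers. One topic that crosses 0.05 could then be reported as evidence that blogshots change expectations or intentions. The study objective names expectations beside awareness and knowledge, so such a result would carry weight.

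The opposite error is also at stake. A moderate shift across all three topics that an arm was taught could be missed question by question, because each test rests on one answer per parent.

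**Working it through.** **1. The plan's own sample size.** Inputs: SD 2.0, 80% power, two-sided 0.05 (two-sidedness taken from the confidence-interval statement). The scale is not given, so I assume that 10% means 1 point on a 10-point scale.

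n per arm = 2 × (1.96 + 0.842)² × (2.0/1.0)² = 62.8, so 63. The t-based version gives 63.8, so 64, as stated. The recruitment target is "We will aim to recruit 180 parents (90 participants per group"), so I use 64 to 90 per arm as the range of completers at follow-up 1.

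**2. Number of tests permitted.** 6 expectation + 6 intention questions = 12 comparisons between arms. Before-after tests and the 7 usability questions are not counted.

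**3. Chance of at least one p<0.05 with no true effect.** If independent: 1 − 0.95¹² = 46.0%. For correlated tests I simulated two-sided z-tests with a common correlation:

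| Assumed correlation | 12 tests | 6 tests (one outcome) |
|---|---|---|
| 0 | 46% | 26% |
| 0.2 | 43% | 25% |
| 0.3 | 40% | 24% |
| 0.5 | 32% | 21% |
| 0.7 | 23% | 16% |

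**4. Detectable shift for one question.** Assume yes/no answers and a 50% reference rate. The 80%-power shift d solves

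d × √n = 1.96 × √(2p̄(1−p̄)) + 0.842 × √(p₁(1−p₁) + p₂(1−p₂)), with p₁ = 0.50, p₂ = 0.50 + d and p̄ their mean.

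- n = 64: (1.346 + 0.560)/8 = 0.238, about 24 points.
- n = 90: (1.357 + 0.570)/9.487 = 0.203, about 20 points.

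For reference rates of 20% to 80% and 64 to 90 per arm, the range is about 14 to 25 points.

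**5. A three-question score for one topic set.** The mean of three yes/no answers with inter-item correlation r has SD = 0.5 × √((1 + 2r)/3), which is 0.316 at r = 0.1, 0.365 at r = 0.3 and 0.447 at r = 0.7. Power for a 15-point shift on all three topics is Φ(0.15/(SD × √(2/n)) − 1.96), before any gain from baseline adjustment:

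| Measure | 64 per arm | 90 per arm |
|---|---|---|
| One question | 40% | 53% |
| Score, r = 0.1 | 77% | 89% |
| Score, r = 0.3 | 64% | 79% |
| Score, r = 0.7 | 48% | 61% |

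**6. Why a six-question total fails.** Suppose each arm gains 15 points on each of its own three topics and nothing on the others. The total rises by 3 × 0.15 = 0.45 in both arms, and the difference between arms is 0. On the Group A topic set alone, Group A gains 0.45 and Group B gains 0, and the difference is kept.

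**7. Error rate with four scores.** Two outcomes by two topic sets give four comparisons: 1 − 0.95⁴ = 18.5% if independent, and less if they are correlated.

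**The case against.** A reader might infer that the plan prescribes 12 separate tests. It does not. The Outcomes section treats expectations and intentions as domains, and the only comparison it spells out for expectations is baseline against follow-up. The t-tests in the analysis section would suit a domain score. With one score per outcome, the false-positive chance would be at most 1 − 0.95² = 9.75%. It stands that separate testing is permitted rather than planned. The escape through one score per outcome is weaker than it looks, because a six-question total cancels in this design (step 6).

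A reader might also take a false-positive chance of 40% to 46% and a detectable shift of 24 points as properties of the trial. The first needs a correlation of 0.3 or less. Higher values are credible, since both sets of questions cover the same topics and most topics concern antibiotics. The second needs yes/no answers, a 50% reference rate and only 64 completers per arm. None of these is documented for these questions, and graded answers would make that calculation inapplicable.

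Finally, these are secondary outcomes in a small educational trial, and confidence intervals are already required throughout. Strict error control over every secondary question is partly a matter of judgement. That supports reporting single questions as estimates. It does not support leaving the score undefined under a general p<0.05 rule.

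**Conclusion.** The plan defines neither a score nor a unit of analysis for two of its three secondary outcomes, and its single threshold lets any of up to 12 single-question comparisons be declared significant. If all 12 were run with no true effect, the chance of at least one false positive would be about 23% to 46%, depending on a correlation that I have assumed. One yes/no question would have 80% power only for a shift of about 20 to 24 points at a 50% reference rate. The documents do not show that separate testing is intended, so these figures measure what the plan allows, not what it will do.

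The remedy goes beyond supplying a missing detail. The scores must follow the topic sets, because each arm is the control for the other arm's topics, and the baseline answers already collected should enter the comparison.

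**What to change.** - For each outcome, form one score per three-topic set. Fix the coding before the data are seen, and keep graded answers if the format is graded.
- Compare arms at follow-up 1 by ANCOVA with the matching baseline score as covariate.
- Limit significance claims for expectations and intentions to these four scores. Either adjust across the four (for example by Holm), or state that the unadjusted false-positive chance is up to 18.5%.
- Report the 12 single questions and the 7 usability questions as estimates with 95% confidence intervals and no significance claim.
- Before defining the sets, reconcile the topic assignment. The group lists under Study Design: RCT place acute asthma exacerbations in Group A and bronchiolitis in Group B. The Knowledge Questions paragraph places bronchiolitis in Group A and asthma exacerbations in Group B.

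The cost is wording only, with no new data. No single topic could then be called significant on its own. The gain in power shrinks if the questions are highly correlated or if only one topic of a set shifts, and Holm adjustment would take back some of it.
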